6.5.3	Visit 3: Week 2 (\pm 2 days)	25
6.5.4	Visit 4: Week 4 (\pm 2 days)	25
6.5.5	Visit 5: Week 6 (\pm 2 days)	26
6.5.6	Visit 6: Week 8 (\pm 2 days)	26
6.5.7	Visit 7: Week 10 (\pm 2 days)	26
7	STATISTICAL PLAN	26
7.1	SAMPLE SIZE DETERMINATION	26
7.2	STATISTICAL METHODS	27
7.3	SUBJECT POPULATION(S) FOR ANALYSIS	27
8	SAFETY AND ADVERSE EVENTS	27
8.1	ADVERSE EVENT DEFINITIONS	27
8.2	CLASSIFICATION OF ADVERSE EVENTS BY SEVERITY	28
8.3	CLASSIFICATION OF ADVERSE EVENTS BY RELATIONSHIP TO STUDY TREATMENT	28
8.4	ACTION(S) TAKEN	29
8.5	OUTCOME	29
8.6	ADVERSE EVENT REPORTING	29
8.7	SERIOUS ADVERSE EVENT REPORTING	29
8.8	IN CASE OF AN EMERGENCY	30
8.9	DATA SAFETY MANAGEMENT PLAN	30
8.10	STUDY OVERSIGHT	30
9	CONFIDENTIALITY	31
10	SOURCE DOCUMENTS	31
10.1	RECORDS RETENTION	31
11	ETHICAL CONSIDERATIONS	31
12	STUDY FINANCES	32
12.1	FUNDING SOURCE	32
12.2	CONFLICT OF INTEREST	32
12.3	SUBJECT STIPENDS OR PAYMENTS	32
13	REFERENCES	33

SCHEDULE OF VISITS AND PROCEDURES

	Screening	Day 1 (Pre-Dose)	Day 1 (Post-Dose)	Week 2	Week 4	Week 6	Week 8	Week 10
Informed Consent	X							
Demographic Information	X							
Medical History/Con Meds	X							
Ophthalmic/Dry Eye History	X							
Vital Signs		X		X	X	X	X	X
Ophthalmic Examination (Slit lamp)	X	X		X	X	X	X	X
Ocular surface redness score	X	X		X	X	X	X	X
Schirmer 1 test and Rose Bengal staining	X						X	
Pregnancy Test (urine)*	X							
Best Spectacle Corrected Visual Acuity		X						X
Randomization visit		X						
First Study Medication		X						
Drug dispensation visits			X	X	X	X		
Instruction on study medication self-administration			X					
Ocular Surface Disease Index (OSDI)		X		X	X	X	X	X
Visual Analogue Scale (VAS)			X	X	X	X	X	
Physical inspection of nose & oropharynx				X	X	X	X	X
Clinical Global Impression (CGI)		X		X	X	X	X	X
Subject Global Assessment (SGI)		X		X	X	X	X	X
Adverse Events/ Concomitant Medications		X	X ⁺⁺	X	X	X	X	X

*If applicable ++ AEs only

ABBREVIATIONS

AE	Adverse Event
APC	Antigen-presenting cells
BSCVA	Best Spectacle Corrected Visual Acuity
EC	Ethics Committee
eDNA	Extracellular DNA
CNL	Corneal Neurobiology Laboratory
CRF	Case Report Form
CGI	Clinical Global Impression
DCF	Data Clarification Form
DED	Dry Eye Disease
DNase I	Deoxyribonuclease I
FDA	Food and Drug Administration
FVC	Forced vital capacity
GCP	Good Clinical Practice
ICH	International Conference on Harmonization
IB	Investigator's Brochure
IOP	Intraocular pressure
IRB	Institutional Review Board
KCS	Keratoconjunctivitis sicca
Net	Neutrophil extracellular trap
OSDI	Ocular Surface Disease Index
Otc	Over the counter
QID	Four times per day
rhDNase1	Recombinant human deoxyribonuclease I
SAE	Serious Adverse Event
SGL	Subject Global Assessment
SP	Substance P
UIC	University of Illinois at Chicago
VA	Visual Acuity
VAS	Visual Analog Scale

Study Summary

Title	A Phase I/II Randomized Placebo-Controlled, Double-Blind Single-Center, tolerability and preliminary efficacy clinical trial of recombinant human deoxyribonuclease (rhDNase) eye drops in patients with dry eye disease.
Short Title	DNase treatment for dry eyes
Protocol Number	UIC-CNBL-1001
Phase	Phase I/II
Methodology	Double-blind
Study Duration	10 weeks
Study Center(s)	Single-center
Objectives	To evaluate the tolerability and preliminary efficacy of rhDNase1 eye drops in patients with Dry Eye Disease.
Number of Subjects	72 (study drug at least 30, placebo at least 30)
Diagnosis and Main Inclusion Criteria	Men and women ≥ 18 years of age with a diagnosis of established Dry Eye Disease, with Schirmer I < 10 , Ocular surface staining ≥ 1 and OSDI mild (≥ 13).
Study Product, Dose, Route, Regimen	Study drug: rhDNase1 (Pulmozyme®), 0.1% eye drops four times a day for eight weeks. Control: drug vehicle eye drops four times a day for eight weeks.
Duration of administration	8 weeks
Reference therapy	None
Statistical Methodology	Descriptive statistics will be used for all primary and safety endpoints, when appropriate. A Wilcoxon test will be used to compare changes in subjective symptoms from Baseline to follow-up values at 2 weeks, 4 weeks, 6 weeks, 8 weeks and 10 weeks. Primary efficacy measure is the change in the OSDI reported between Baseline and Week 8. Primary safety measure is the proportion of patients at week 8 who were able to successfully complete a full eight weeks of therapy with topical administration four times per day (q.i.d).

1 Introduction

This document is a protocol for a human research study. This study is to be conducted according to US and international standards of Good Clinical Practice (FDA Title 21 part 312 and International Conference on Harmonization guidelines), applicable government regulations and Institutional research policies and procedures.

1.1 Background

Keratoconjunctivitis sicca (KCS) or Dry Eye Disease is a disease of the surface of the eye, tear film and related ocular tissues. Millions of people suffer from one form of the disease or another and its prevalence increases with age. Dry Eye Disease sufferers experience a broad range of symptoms including discomfort, irritation, burning, itching, redness, pain, gritty feeling, foreign body sensation, blurred vision and ocular fatigue. These symptoms can progress and lead to ulceration and perforation of the cornea, lead to increased ocular infections and even result in an inability to produce emotional tears.

Dry eye as a disease entity is considered to fall in to two broad categories: 1) Aqueous tear deficiency (as seen in Sjögren's syndrome) and 2) increased tear evaporation (as seen with infectious blepharitis, lid abnormalities, or associated with wearing contact lenses).

Until recently, the only treatment options for Dry Eye Disease (DED) were palliative in nature and limited to lubricating eyedrops or punctual occlusion procedures, which attempt to supplement natural tears, or improve the resistance time of the limited quantity of tears produced naturally by the patient.

Although DED pathogenesis is not fully understood, inflammation has a prominent role in DED symptom development and amplification.^{1,2} The current paradigm suggests that ocular surface inflammation is triggered by surface epithelium stress caused by tear hyperosmolarity. Inflammation is sustained by activated antigen-presenting cells (APCs) and T cells via the afferent and efferent limbs of the adaptive immune system.^{3,4}

The immunopathological events that sustain the systemic adaptive immune response in DED have been characterized.^{2,4} However, the mechanisms that activate the adaptive immune response are poorly understood. Ocular surface epithelial stress is a key initial event and a major source of innate cytokines and chemokines that can damage epithelial cells and activate APCs. Tear hyperosmolarity is recognized as an important stressor. However, tear replacement to decrease osmolarity provides limited therapeutic benefit. Therefore, additional stressors may activate DED ocular surface inflammation and link the innate and adaptive immune mechanisms.

The ocular surface epithelium undergoes continuous, dynamic turnover^{5,6}, which is increased in DED patients.⁷ Superficial corneal cells are shed into the precorneal tear film.^{8,9} The corneal epithelial cell shedding process, or desquamation, is regulated by apoptotic mechanisms.¹⁰ Dead and dying cells release extracellular DNA (eDNA), a type of damage-associated molecular pattern molecule, that can stimulate the innate immune system and link it to adaptive immune system.^{11,12} eDNA strands have been reported in corneal filaments, which are frequently present on the corneas of patients with severe DED.¹³ Desquamated cells in the precorneal tear film are a potential source of eDNA. Tear fluid nucleases, including lipocalin and DNase1, can hydrolyze and clear eDNA from the precorneal tear film.^{14,15} Additionally, tear fluid contains several neutrophil extracellular trap (NET) components. Neutrophils undergo a low level of recruitment on the ocular surface,¹⁶ and numerous neutrophils are

present in the tear film during ocular surface inflammation.¹⁷ Neutrophil elastase and histone proteins have also been reported in tear fluid.¹⁸ Taken together, these reports document the presence of eDNA, histones, neutrophils, neutrophil elastase, and nucleases in tear fluid and suggest mechanisms exist for the continual production and clearance of eDNA in the precorneal tear film.

We have performed investigations in dry eye disease patients that have yielded several important findings.¹⁹ First, eDNA and NETs are present in excessive amounts on the ocular surface of patients with severe, tear-deficient DED. Immunolocalization experiments revealed that the molecular components of NETs include histones, cathelicidin, and neutrophil elastase. Next, using a DNA digestion assay, we determined that tear fluid nuclease activity was >0.05 Kunitz units. Using a FRET-based assay, we found that tear fluid nuclease activity was reduced in DED patients. We determined that DNase I is a DNA hydrolyzing nuclease present in lacrimal glands and a normal concentration in tear fluid is 3.14 ng/ml, similar to that in serum and saliva. We also determined that mucoid films are present on the ocular surface or inferior conjunctival fornix in some patients with severe DED (particularly with GVHD) and are rich in neutrophils, eDNA, and NETs. Finally, exfoliated ocular surface cells from DED patients had increased expression of inflammatory cytokines and eDNA signaling pathway genes.

Taken together, these findings suggest that in healthy eyes, eDNA is produced in the precorneal tear film and cleared by tear fluid nucleases. In patients with severe DED, tear fluid nuclease deficiency allows eDNA, neutrophils, and NETs to accumulate in the precorneal tear film and cause ocular surface inflammation. The practical implication of our findings is the suggestion of new therapeutic interventions based on clearing eDNA, NETs, and their molecular components from the ocular surface, as well as inhibiting eDNA signaling pathway gene expression. These findings have been published in *Investigative Ophthalmology and Visual Sciences*¹⁹, and were quoted as a new insight into dry eye inflammation by an editorial comment in the same publication.²⁰ These findings underpin the basis of this research protocol.

1.2 Agent

The agent used in this study is recombinant human deoxyribonuclease I (rhDNase1). This agent is FDA approved for human use and is marketed as Pulmozyme (Genentech, San Francisco, CA). Pulmozyme is a sterile, clear, colorless, highly purified solution of recombinant human deoxyribonuclease I (rhDNase1). The protein is produced by genetically engineered Chinese Hamster Ovary (CHO) cells containing DNA encoding for the native human protein, deoxyribonuclease I (DNase1). Fermentation is carried out in a nutrient medium containing the antibiotic gentamicin, 100–200 mg/L. However, the presence of the antibiotic is not detectable in the final product. The product is purified by tangential flow filtration and column chromatography. The purified glycoprotein contains 260 amino acids with an approximate molecular weight of 37,000 daltons. The primary amino acid sequence is identical to that of the native human enzyme.

Each Pulmozyme single-use ampule has 2.5 mL of the solution. The aqueous solution contains 1.0 mg/mL dornase alfa (0.1%), 0.15 mg/mL calcium chloride dihydrate and 8.77 mg/mL sodium chloride. The solution contains no preservative. The nominal pH of the solution is 6.3.

Pulmozyme is approved by FDA for use in humans. Daily administration of Pulmozyme® (dornase alfa) Inhalation Solution in conjunction with standard therapies is indicated in the management of cystic fibrosis patients to improve pulmonary function. In patients with an FVC \geq 40% of predicted, daily administration of Pulmozyme has also been shown to reduce the risk of respiratory tract infections requiring parenteral antibiotics.

When 2.5 mg Pulmozyme was administered by inhalation to eighteen CF patients, mean sputum concentrations of 3 µg/mL DNase were measurable within 15 minutes. Mean sputum concentrations declined to an average of 0.6 µg/mL two hours following inhalation. Inhalation of up to 10 mg TID of Pulmozyme by 4 CF patients for six consecutive days, did not result in a significant elevation of serum concentrations of DNase above normal endogenous levels.^{21,22} After administration of up to 2.5 mg of Pulmozyme twice daily for six months to 321 CF patients, no accumulation of serum DNase was noted. Pulmozyme, 2.5 mg by inhalation, was administered daily to 98 patients aged 3 months to ≤ 10 years, and bronchoalveolar lavage (BAL) fluid was obtained within 90 minutes of the first dose. BAL DNase concentrations were detectable in all patients but showed a broad range, from 0.007 to 1.8 µg/mL. Over an average of 14 days of exposure, serum DNase concentrations (mean ± s.d.) increased by 1.3 ± 1.3 ng/mL for the 3 months to < 5 year age group and by 0.8 ± 1.2 ng/mL for the 5 to ≤ 10 year age group. The relationship between BAL or serum DNase concentration and adverse experiences and clinical outcomes is unknown.

1.3 Preclinical Data

We performed experiments that showed that eDNA, NETs, and neutrophils were present on the ocular surface in DED patients and abundant in mucoid films. NETs consisted of eDNA, histones, cathelicidin, and neutrophil elastase. Tear fluid nuclease activity was significantly decreased in DED patients, whereas the amount of eDNA on the ocular surface was significantly increased. Expression of genes downstream of eDNA signaling, such as TLR9, MyD88, and type I interferon, as well as the inflammatory cytokines interleukin-6 and tumor necrosis factor alpha, was significantly increased in DED patients. Therefore, based on our findings we conclude that extracellular DNA production and clearance mechanisms are dysregulated in DED.¹⁹ Nuclease deficiency in tear fluid allows eDNA and NETs to accumulate in precorneal tear film and results in ocular surface inflammation. These findings point to novel therapeutic interventions in severe DED based on clearance of eDNA, NETs, and other molecular components from the ocular surface. DNase I, an enzyme which selectively cleaves DNA, is one such therapeutic intervention. Our data showed that DNase I is naturally present in the lacrimal glands and tear fluid in humans. The concentration in tear fluid is 3.14 ng/ml. This concentration is similar to that in serum. Serum tear eye drops (containing DNase I) have been topically applied to the eye with significant therapeutic benefit to patients with severe dry eyes. To date there are no reports of direct application of DNase I to the eye.

1.5 Dose Rationale and Risk/Benefits

RhDNase1 1mg/ml (0.1%) will be applied topically to the ocular surface as eye drops. This is the same dose as is currently in use in patients with Cystic Fibrosis. The drug formulation is being used unchanged. This dose has been effective in reducing eDNA content when given to patients with cystic fibrosis. We do not expect any serious adverse events with this dose.

Drugs are routinely applied topically to the ocular surface as eye drops because of easy access to the ocular tissues and good drug bioavailability. Therefore, we will use rhDNase1 topically. We have chosen an eight week duration of therapy because we expect rhDNase1 to be used continually; eight weeks of treatment will give us better data to predict side effects during long-term use. Since rhDNase1 is not expected to increase the production of natural DNase I, but rather it only supplements it so that the imbalance of decreased tear fluid DNase I is corrected, we expect long-term use of rhDNase1.

RhDNase is currently used as an inhaled drug in adults and children with cystic fibrosis. Patients with cystic fibrosis have experienced a change in or loss of their voice, discomfort in the throat, chest pain, red watery eyes, rash, dizziness, fever, or runny nose. Most of these are systemic side-effects that are not generally seen with eye drops. These side effects are usually mild and short-lived.

The most likely discomforts a subject may experience by having RhDNase administered as eye drops are eye burning or irritation, red watery eyes, or feeling like there is something in the eye. To see how subjects react to the study medication, their first dose will be given by the investigator in the clinic itself. Afterwards subjects will be asked to rate tolerability of the drug on the Visual Analogue Scale. Also, at each) visit, subjects will be asked to complete the Visual Analogue Scale.

An allergic reaction to the drug cannot be predicted beforehand. In event of an allergic reaction, the drug will be stopped immediately, and symptoms will be managed appropriately depending on the severity of the reaction.

Restasis, a drug used to treat DED, is held during the 14 day wash-out period and over the entire course of the study. Holding Restasis may increase the subject's risk of worsening DED.

Participants randomized to the placebo have a risk of worsening dry eye disease. All study subjects will be encouraged to contact the research team immediately if they experience worsening of their DED.

No psychological, social, legal, or financial risk is expected from participating in the research.

There is always a risk of a loss of confidentiality.

2 Study Objectives

The objective of this study is to establish whether patients with Dry Eye Disease are able to tolerate receiving rhDNase1 0.1% eye drops four times a day for eight weeks (primary tolerability objective) and to investigate the preliminary efficacy of rhDNase1 topical eye drop solution 0.1% in treating Dry Eye Disease (primary efficacy objective).

3 Study Design

3.1 General Design

This will be a Randomized controlled trial, in which a total of 72 patients will be enrolled at 1 clinical site. Subjects will be randomly assigned to one of two groups (#1, #2), with at least 30 subjects per group. Group #1 will be given placebo (drug vehicle- eye drops without rhDNase 0.1%) and Group #2 will be given study drug (rhDNase 0.1%).

Patients with established Dry Eye Disease will be approached by a member of the research staff to determine if the patient might be interested in participating in a research study. If the patient is interested, the research staff member will describe the study. If the patient is willing to enter the study, the study will be discussed and the patient will be asked to sign the informed consent form. Consent will be obtained prior to screening to determine eligibility. Screening procedures include documentation of prior Dry Eye Disease. Eligible patients will be enrolled in the study.

All enrolled subjects will receive their first dose of test medication (placebo/ study drug) on study Day 1 in the doctor's office and after completion of the study assessments, will have the topical eye drops dispensed for self-administration. See Section 5.4 *Preparation and Administration of Study Drug* for details.

Subjects will be provided with diaries to record the time of each dose and will also be asked to record any adverse symptoms. In addition, they will be asked to make a note of any missed doses together with the reason for the omission. Subjects will return two weeks later on Day 14 for further study assessments, thereafter at 4 weeks, 6 weeks and 8 weeks (the last day of treatment), and again at 10 weeks after two weeks of no treatment with study drug for the final study assessments.

3.2 Primary Study Endpoints

Primary Efficacy End Point: The primary end points after 8 weeks of treatment include the following: (1) the change in the Ocular Surface Disease Index (OSDI) which is a patient subjective rating scale; the Clinical Global Impression (CGI) of change in dry eye disease symptoms (physician's rating) and Subject Global Assessment (SGA) of overall change from baseline (patient's rating) will serve as anchors to OSDI, as has been described previously²⁹; (2) a mean reduction in ocular surface staining as measured by Rose Bengal dye staining and (3) the change in ocular surface redness score OR slit-lamp examination.

Primary Tolerability End Point: The change in the test substance tolerance between Day 1 (post-dose) and at weeks 2, 4, 6 and 8.

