3.2.4 Efficacy End Point: Ocular surface Rose Bengal dye staining score

Ocular surface staining will be assessed using Rose Bengal dye. Saline moistened 1% Rose Bengal dye impregnated strips will be used to instill the dye on the inferior palpebral conjunctiva and scoring of corneal and conjunctival staining will be performed by a slit lamp examination after 15 seconds using the grading system described by the 1995 NEI workshop.³⁰ Corneal staining will be graded in 5 zones

and conjunctival staining will be graded in 6 zones. Each zone will be graded from 0 to 3 based on the density of punctate staining. The final staining score will be the sum of individual scores from all 11 zones (5 corneal, 6 conjunctival). The scoring pattern is represented below.

[figure not shown]
Complete ocular surface staining clearance means absence of any punctate or confluent staining with Rose Bengal dye defined as Rose Bengal staining score of 0.

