3.2.5 Efficacy End Point: Ocular surface redness score

Ocular surface redness (nasal or temporal) will be assessed using the Validated Bulbar Redness grading scale (VBR).³¹ The VBR consists of a set of ten images illustrating different degrees of ocular surface redness (OR), ranging from normal to severe, and each image is assigned a value in an order of ascending severity. Colored copies of these images will be made using a single printer and constant settings and put up in all the examination rooms. Subjects will be examined by a slit-lamp at 10X magnification using direct diffuse illumination (slit fully opened, angled at 30°- 50° approximately; at half illumination intensity with rheostat set to maximum voltage) and the bulbar conjunctival injection of the subject's eye (nasal and temporal) will be compared to the reference images and graded accordingly. To maintain uniformity, all subjects will be graded by a single physician (Principal Investigator) under constant illumination conditions. The subjects will be asked to look at nasal or temporal fixation marks while the physician will examine the temporal or nasal bulbar conjunctivae, respectively.

Photographic anchors and their respective grades for ocular surface redness are shown below:

□

[figure not shown]

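### The synopsis names one primary efficacy measure and section 3.2 numbers three; nothing says which prevails, and no between-group method is named behind the promised drug-versus-placebo interval

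*Combined protocol and SAP*

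**What the plan says.** The Statistical Methodology row of the synopsis (Study Summary) gives a single measure: "Primary efficacy measure is the change in the OSDI reported between Baseline and Week 8". Section 3.2 opens under a singular heading but uses the plural: "The primary end points after 8 weeks of treatment include the following: (1) the change in the Ocular Surface Disease Index (OSDI"). Its second item is "2) a mean reduction in ocular surface staining as measured by Rose Bengal dye staining". Its third item reads "3) the change in ocular surface redness score OR slit-lamp examination". It gives the Clinical Global Impression (CGI) and Subject Global Assessment (SGA) the role of anchors to OSDI. Even so, sections 3.2.2 to 3.2.5 head CGI, SGA, staining and redness each as an efficacy end point, for example "Efficacy End Point: Ocular surface Rose Bengal dye staining score". The secondary list in section 3.3 contains complete staining clearance, but neither the staining score nor redness.

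On testing, the synopsis says: "A Wilcoxon test will be used to compare changes in subjective symptoms from Baseline to follow-up values". Section 7.2 specifies:

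- descriptive statistics for primary and secondary end points;
- a paired Wilcoxon signed-rank test for OSDI, baseline against each later visit;
- a chi-square test between the two groups for an investigator's rating scale and for concomitant medication changes;
- a two-sided 5% threshold for all comparisons;
- control for chance baseline imbalance between groups;
- 95% confidence intervals, drug versus placebo, for primary efficacy, primary safety and the secondary end points.

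The aim in section 2 is "to investigate the preliminary efficacy of rhDNase1 topical eye drop solution 0.1% in treating Dry Eye Disease (primary efficacy objective").

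**The concern.** The three numbered end points are not restatements of one another. OSDI is reported by the patient; staining and redness are signs graded by an examiner. They can disagree at week 8, and the plan does not say which would then be the primary efficacy result.

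The test named for OSDI compounds this. A significant fall from baseline within the drug arm is not evidence against vehicle, because symptoms may also fall on vehicle. As the text stands, any of three outcomes, or a within-arm change, could be presented as the primary efficacy finding, and the choice could be made after the results are known.

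**Working it through.** **1. Which text prevails.** The synopsis gives one measure and section 3.2 gives three. Some wording leans towards OSDI: the synopsis itself, the singular heading and OSDI-first order in section 3.2, and the singular reference to primary efficacy in section 7.2. Section 3.2 cannot be read as a loose list that includes secondaries, because section 3.3 holds neither the staining score nor redness. No section settles the matter.

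**2. Which test compares the arms.**

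| End point | Named test | Compares arms? |
|---|---|---|
| OSDI, section 7.2 | Signed-rank against baseline | No |
| Symptoms, synopsis | Wilcoxon, type not stated | Unclear |
| Staining score | None named specifically | – |
| Redness | None named specifically | – |
| Investigator's rating scale | Chi-square | Yes |

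The investigator's rating scale is not defined. CGI is the natural reading. Redness is also graded by the Principal Investigator (section 3.2.5), but it is an ordered image scale, and the text describes the chi-square variables as qualitative. The promised interval does compare the arms, but it has no stated estimator or model.

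**3. Size, as an illustration only.** The plan gives no figure to reproduce. Assume one valid two-sided 5% between-group test for each of three end points, equal correlation rho between the test statistics, no true effect, and that any one significant result counts. The correlations are assumptions; the documents give none.

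- Independent, either direction: 1 − 0.95³ = 1 − 0.8574 = 0.1426.
- Independent, favouring the drug only: 1 − 0.975³ = 1 − 0.9269 = 0.0731.
- Correlated: numerical integration over a shared normal factor, critical value 1.96.

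| rho | Either direction | Favouring drug | Ratio to 2.5% |
|---|---|---|---|
| 0 | 14.3% | 7.3% | 2.9 |
| 0.3 | 13.6% | 6.8% | 2.7 |
| 0.5 | 12.5% | 6.3% | 2.5 |
| 0.7 | 10.9% | 5.5% | 2.2 |
| 0.9 | 8.4% | 4.2% | 1.7 |
| OSDI alone | 5.0% | 2.5% | 1.0 |

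If all three had to succeed, there would be no inflation.

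**4. The within-arm route.** Take 30 completers per arm (section 7.1) and assume that both arms improve equally, with no drug effect. If p is the chance that a signed-rank test is significant in one arm, then significance on drug but not on vehicle has probability p(1 − p). Simulated p for assumed shifts of 0.2, 0.36, 0.5 and 0.7 SD is 0.181, 0.460, 0.745 and 0.953. This gives 0.148, 0.248, 0.190 and 0.045, so roughly 4% to 25% of such trials would show a misleading contrast.

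**The case against.** The best defence is that this is a Phase I/II trial seeking preliminary efficacy. Statistics are largely descriptive, no power is stated, and no passage sets a success rule or a go/no-go decision. Strict familywise control is therefore not owed, and that stands. What remains is that section 7.2 still sets a significance threshold and that efficacy is a primary objective, so the reader needs to know which comparison carries it.

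A second defence is that the arms will be compared. This also stands in part. A 95% interval for a between-group difference normally carries the same information as a two-sided 5% test, and it would be reported beside any within-arm result. A reader might infer that the plan contains no drug-versus-vehicle comparison; the promised interval, the baseline control and the chi-square test contradict that. What is missing is the method behind the interval and the end point it applies to.

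A reader might also count more than three primaries. Section 3.2 makes CGI and SGA anchors, so their headings are a labelling fault. Nor does the third item establish a separate slit-lamp end point. Section 3.2.5 uses OR as an abbreviation ("illustrating different degrees of ocular surface redness (OR") and grades redness at the slit lamp, so the phrase may be a garbled label. Section 3.4.2, however, describes a much broader slit-lamp examination, and the documents do not decide between the two readings.

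**Conclusion.** The concern holds in this limited form. The conflict between the synopsis and section 3.2 is plain on the text, and so is the absence of a named estimator or model for drug versus vehicle on OSDI, staining or redness. Confidence in both is high; how to read the third item is left open.

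The inflation figures (14.3% down to 8.4% in either direction, 7.3% down to 4.2% favouring the drug) depend on an any-one-suffices rule, valid tests and assumed correlations. A reader might infer that the trial has a 14% false-positive rate. The documents do not support that, since they state no such rule and clearly name no such tests. The figures show what leaving the choice open could cost. The sponsor should correct this, but it does not invalidate the design. The primary tolerability and primary safety end points are unaffected.

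**What to change.** Before unblinding:

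1. Align section 3.2 with the synopsis: the primary efficacy end point is the drug-versus-vehicle difference in OSDI change from baseline to week 8.
2. In the synopsis and section 7.2, name the between-group analysis behind the promised 95% interval. One example is ANCOVA of week 8 OSDI change on treatment and baseline OSDI; a rank-based equivalent would also serve. State how subjects without a week 8 OSDI enter it: section 7.3 admits anyone with two weeks of treatment and a week 2 visit, and section 4.4.2 has early withdrawals complete the week 10 procedures early.
3. Label the signed-rank tests against baseline, and OSDI at weeks 2, 4, 6 and 10, as supportive.
4. Move the week 8 staining score and redness to section 3.3 with between-group 95% intervals. Relabel sections 3.2.2 to 3.2.5 so that CGI and SGA are described as anchors and no other efficacy measure sits under the primary heading.
5. Have the sponsor say whether the OR in item 3 abbreviates ocular redness or introduces an alternative outcome, and reword the item to one defined measure.

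As an alternative to steps 1 and 4, keep all three as primary, fix an order, an alpha split or an all-must-succeed rule, name the between-group test for each, and correct the synopsis.

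The cost is wording in the synopsis and in sections 3.2, 3.2.2 to 3.2.5, 3.3 and 7.2, with no new data or visits. The sponsor gives up the option to present staining or redness alone as the primary efficacy result; under the alternative it must commit to a multiplicity rule in advance.
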